4.2 Exclusion Criteria

- a) Serum potassium ≥ 6.5 mEq/L within 2 months prior to screening
- b) Unscheduled dialysis for hyperkalemia within the 3 months prior to screening
- c) Pre-dialysis hypotension defined as pre-dialysis SBP <100 mm Hg (seated measurement) within 4 weeks prior to the screening visit
- d) Recurrent intra-dialytic hypotension defined as either of the following:
 - o systolic blood pressure <80 mm Hg during ≥ 3 dialysis sessions in the 30 days prior to the screening visit, or
 - o treatment for hypotension or symptoms of hypotension during ≥ 3 dialysis sessions in the 30 days prior to the screening visit. For this criterion, hypotension is defined as systolic blood pressure <100 mm Hg.
- e) Mitral valve repair or replacement
- f) Severe mitral valve disease by echocardiography, coronary angiography or cardiac magnetic resonance imaging
- g) Anticipated kidney transplant, change to peritoneal dialysis, or transfer to another dialysis unit within 6 months
- h) Expected survival <6 months
- i) Allergy to study medications (ISD, HY, adenosine or dipyridamole)
- j) Active use of sildenafil, vardenafil or tadalafil
- k) Current severe aortic stenosis or other cause of LV outflow obstruction
- l) Pregnancy, anticipated pregnancy, or breastfeeding, confirmed by serum pregnancy test on the day of PET scan
- m) Incarceration
- n) Participation in another intervention study
- o) Use of monoamine oxidase inhibitors
- p) Contraindication to adenosine including

- 2nd or 3rd degree heart block, sick sinus syndrome or symptomatic bradycardia (without a functioning pacemaker)
- moderate or severe asthma
- chronic obstructive pulmonary disease

q) Active use of any of the study medications unless participant and physician willing to discontinue prior to enrollment.

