7.1 Sample Size Determination

Sample size considerations were framed using standard study design parameters to ensure 80% power to detect pre-specified effect sizes utilizing intermediate outcomes. However, for this early phase pilot study, the primary focus is directed at providing pilot efficacy, safety and feasibility information, with no attempt to create critical test result regions for standard hypothesis testing. Results will nevertheless provide preliminary estimates needed to guide design of subsequent, more robust studies and will provide information on safety and tolerability events occurring at high event rates which can be incorporated into the design of further studies.

With 8 participants per group, there will be 80% power to detect a change in CFR of 0.75 (unitless measure), assuming a common standard deviation for change in CFR of 0.5¹³⁸⁻¹⁴³. Assuming the common SD of E' is 2.0 cm/s and baseline is 5.8 ± 1.8 cm/s^{39, 144-146}, we will be able to detect a difference of 3.0 cm/s with 80% power. Changes of this magnitude have been observed in other settings^{144, 147, 148}. Baseline variables will be presented using standard descriptive statistics according to distribution. P<0.05 will be considered significant without correction for multiple comparisons given the pilot nature of this proposal.

Although the detectable change in each effect measure is large, detectable differences are, as noted above, clinically relevant. Further, given the pilot nature of this study, additional trials will be required regardless of whether a significant difference in the efficacy measures is detected. Point estimates and standard deviations around these measures will provide the needed estimates of expected change so that more robust studies can be designed.

It is similarly noted that under the proposed sample size, estimates of safety and tolerability event rates will provide relatively crude estimates of the true event rates. Confidence intervals around estimated event rates based on various observed event rates within the treatment (or control arm) will be large and are provided below for a range of detected event rates (Table 1). As shown in Table 2, power to detect event rates $\geq 20\%$ will be good while power to detect lower event rates within each study arm will be limited for events with a true rate <15%.

Table 1. Confidence interval for estimated event rates within each study arm

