7.2 Randomization and Stratification

To ensure balance in treatment assignments within potential confounders, a stratified randomization procedure, based on LVEF <=45% will be implemented. Within each of these strata, participants will be randomly allocated to the ISD/HY or placebo in a ratio of 1:1.

In order to maintain blinding, ISD, HY, and placebo preparations for each arm will have an identical appearance, and the same number of tablets will be prescribed for each participant. The treatment assignment code, corresponding to each treatment identifier number, will be known only to the IDS, until the completion of treatment and data collection on all participants. This information may also be known to the dispensing pharmacists. The study participants, and all other members of the investigative team, will remain blinded to the treatment assignment, including the investigator, the biostatisticians, the study nurses, and referring physicians.

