7.4.1 Descriptive Analysis

Standard descriptive statistics will be used to summarize baseline characteristics and study outcome measures at each follow-up visit, both overall and within each treatment group. Examination of baseline characteristics will include estimates of the distribution of age, race, and other demographic characteristics, lab measures and study center. Summary statistics such as means, medians, and ranges will be produced for all measured variables. Frequencies will be computed for all categorical and ordinal variables. Graphical methods including stem-and-leaf diagrams and boxplots will be used to examine distributions, identify potential influential points, and guide in the choice of transformations, if warranted. The balance of baseline measures across the treatment groups will be compared using appropriate k-sample tests, including X-Squared tests and Fisher's exact tests.

Analysis of Primary Efficacy and Safety Outcomes Mean \pm standard deviation or median (interquartile values) of baseline and end of study measurement in the primary endpoint E' will be presented. Change in E' velocity or CFR at 26 weeks will be assessed and reported quantitatively, and descriptive statistics for absolute and % change will be provided. Mixed effects linear regression models with baseline covariate adjustments will be used for assessment of treatment effects. Model assumptions regarding homoscedasticity and normality will be examined using standard techniques.

For the safety endpoints, tables with percent incidence and incidence rate (for events that can occur more than once during follow-up) will be prepared. Differences in incidence and incidence-rate will be assessed using logistic regression or Poisson regression with factors for assigned treatment and the stratification variable. In particular, for safety endpoints, we will investigate the potential shift in blood pressure in control and treatment groups with monthly measure of blood pressure. We will use mixed effects linear regression models to assess the direction and time averaged magnitude of change in potassium, with and without controlling for baseline covariates. The proportion of serious hypotension in treatment and control groups will be compared with Chi-square test or Fisher's exact test.

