The primary analysis will examine the intention to treat population. Exploratory analyses will be repeated in the as-treated, all-treated and per-protocol populations (see **Section 7.3**) using analogous techniques. $P<0.05$ will be considered significant in all analyses.

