8.3.2 Non-Reportable Events

The hemodialysis population is characterized by frequent laboratory testing and a high rate of peridialytic hypotensive events requiring change in the dialysis prescription, adjustment of dry weight or change in dialysis-related medications. Due to the unique nature of this population, the following events are considered routine aspects of chronic dialysis therapy and they will not be considered to meet the criteria of SAE in this study except as noted:

- Anemia—will be reported only when hemoglobin <8.0 mg/dL
- Hyperphosphatemia—will be reported only when phosphate >9.5 mg/dL
- Hypocalcemia—will be reported only when serum calcium <7.0 mg/dL
- Hypercalcemia—will be reported only when serum calcium >11.0 mg/dL
- Hyperparathyroidism—will be reported only when PTH>1000 pg/mL
- Hypotension—will be reported only when requiring emergency room visit or hospitalization

- Hyperkalemia—will be reported only when >7.0 mEq/L
- Hypokalemia—will be reported only when <3.0 mEq/L

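### Rates of repeatable safety events are compared by ordinary Poisson regression, which gives intervals that are too narrow and P values that are too small if participants differ in how prone they are to events

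*Combined protocol and SAP*

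**What the plan says.** Section 7.4.1 plans a percent incidence for each safety endpoint and, in addition, an "incidence rate (for events that can occur more than once during follow-up". It then states: "Differences in incidence and incidence-rate will be assessed using logistic regression or Poisson regression with factors for assigned treatment and the stratification variable". The stratification variable is LVEF; section 7.2 says "a stratified randomization procedure, based on LVEF <=45% will be implemented".

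No dispersion term, negative binomial model, participant effect, robust variance, permutation test or exposure offset is named anywhere for event counts. The mixed-effects models in section 7.4.1 are linear. They serve E' and CFR and, on the safety side, potassium.

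Section 7.4.1 assigns serious hypotension to a chi-square or Fisher test. The Study Summary does the same for the incidence of safety events, with emphasis on hypotension.

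Section 7.1 says "P<0.05 will be considered significant without correction for multiple comparisons given the pilot nature of this proposal", and section 7.4.1 adds that this threshold "will be considered significant in all analyses". Section 7.4 says the confidence intervals around adverse event rates are meant to inform later studies.

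**The concern.** A Poisson model for a rate takes the number of events as the information. If a few participants have many events and most have few, the information lies closer to the number of participants, here 16. The model-based standard error is then too small.

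The protocol itself gives reason to expect this for hypotension. Section 3.2.1 (item 4) defines a safety endpoint by hypotension in at least three sessions of the same participant within a rolling 30 days. Exclusion criterion (d) in section 4.2 applies the same idea to "dialysis sessions in the 30 days prior to the screening visit". Section 8.3.2 describes "a high rate of peridialytic hypotensive events" in this population. Dialysis records are reviewed for hypotension at the study visits (section 6.4), so repeat counts can be formed.

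At stake is the comparison of repeatable-event rates, for example intra-dialytic hypotension episodes, hospitalizations or all adverse events. One or two event-prone participants could produce P<0.05 in either direction. The interval carried forward to the next trial would also claim more precision than 16 people can give.

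**Working it through.** **The plan's own figures.** The documents give no figure for the rate comparison. Table 2 in section 7.1 does show which unit the sponsor had in mind for safety: its detection probability is 1 − (1 − p)^8, with 8 participants per arm. For p = 0.05 this gives 1 − 0.95^8 = 0.337 (table: 0.34), and for p = 0.20 it gives 1 − 0.80^8 = 0.832 (table: 0.83). All six rows reproduce. There the participant is the unit; in the Poisson rate model the event is.

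**Inputs.** From the documents: 8 per arm, 1:1 allocation, P<0.05 (taken as two-sided, which the plan does not state), and terms for arm and LVEF stratum. Assumed, because the documents are silent: mean events per participant m = 1, 4 or 8, and gamma heterogeneity k = 0.25, 0.5 or 1.0.

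**Formulas.** With gamma-Poisson counts the variance is m(1 + km), so the variance-to-mean ratio is φ = 1 + km. The plain Poisson interval for the log rate ratio has 1/√φ of the correct width. The large-sample type I error is 2[1 − Φ(1.96/√φ)]. The last column is from simulation with no true effect (20,000 trials per setting, likelihood-ratio test of arm, no stratum). Repeat runs agreed within about 1 percentage point.

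| m | k | φ | Width, 1/√φ | Large-sample error | Simulated error |
|---|---|---|---|---|---|
| 1 | 0.25 | 1.25 | 0.89 | 8% | 9% |
| 1 | 0.5 | 1.5 | 0.82 | 11% | 12% |
| 1 | 1.0 | 2 | 0.71 | 17% | 18% |
| 4 | 0.25 | 2 | 0.71 | 17% | 17% |
| 4 | 0.5 | 3 | 0.58 | 26% | 26% |
| 4 | 1.0 | 5 | 0.45 | 38% | 38% |
| 8 | 0.25 | 3 | 0.58 | 26% | 26% |
| 8 | 0.5 | 5 | 0.45 | 38% | 38% |
| 8 | 1.0 | 9 | 0.33 | 51% | 51% |

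With k = 0 the error is about 5–6%.

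**With LVEF stratum in the model.** This check used a Wald test, an assumed 2 of 8 per arm with low LVEF, means of 3 to 12 and about 2,000 trials per setting. Trials with no events in an arm or stratum were left out. Plain Poisson rejected in 4–5% of trials at φ = 1, 16–17% at φ = 2, 25% at φ = 3 and 37–39% at φ = 5.

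**Candidate remedies, with arm and stratum:**
- Poisson scaled by Pearson χ²/df (not below 1), t reference on 13 df: 2–5%.
- Permutation of participant counts within LVEF stratum: 3–5%.
- Uncorrected sandwich variance with a normal reference: about 9–16%.
- Negative binomial with a t reference on 13 df (about 600 trials per setting): 6–8%, with convergence failures.

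**Invented illustration, unstratified.** Placebo counts are 0, 1, 0, 2, 1, 0, 1, 1 (total 6). Active counts are 0, 1, 12, 2, 0, 1, 1, 1 (total 18). The rate ratio is 18/6 = 3.0.
- Plain Poisson: SE = √(1/6 + 1/18) = 0.471; 95% CI 1.19 to 7.56; P = 0.02.
- Scaled: φ = 54.2/14 = 3.87; SE = 0.471 × √3.87 = 0.928; with t on 14 df, 95% CI 0.41 to 21.9; P = 0.26.

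**The case against.** Five points can be made for the plan.

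1. **The headline hypotension comparison lies elsewhere.** This stands. A reader might infer that the main hypotension result is invalid, but the documents do not support that. The chi-square or Fisher tests and any-event logistic regression count each participant once, so clustering does not touch them.

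2. **The inflation is assumed.** This also stands. No event mean or dispersion is given, and without extra variation there is essentially none. At low counts the result depends on the test: at a mean of 1 the Wald test gives 6–13%, against 9–18% for the likelihood-ratio test. Criterion (d) in section 4.2 and the systolic pressure requirement in section 4.1 (e) remove the most hypotension-prone patients, which may reduce heterogeneity. Differences below those cutoffs, and in response to a vasodilator, remain possible.

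3. **A per-session count is not clearly an endpoint.** This stands in part. The recurrent-hypotension endpoint is defined over a rolling 30 days, and section 8.3.2 restricts the reporting of routine hypotension. Section 2.1, however, lists intra-dialytic hypotension without a threshold, and section 7.4.1 applies rates to any repeatable event. A reader might also reckon about 78 sessions per participant (3 × 26 weeks), but the documents do not state thrice-weekly dialysis, and nothing here relies on it.

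4. **It is a pilot with flexible methods.** Section 7.1 disclaims critical regions, section 7.4 allows methods to be revised, and no stated decision depends on a Poisson P value. This lowers the severity. It does not supply a method, and the intervals themselves are a stated product of the trial.

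5. **Adjustment for the stratification factor is standard.** Agreed. A pre-randomisation hypotension covariate might gain precision, but it costs a degree of freedom among 16 people and is not needed for validity.

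**Conclusion.** The point holds for between-arm comparisons of repeatable-event rates, and only for those. If counts are overdispersed, the named method gives intervals that are too narrow and P values that are too small. The protocol's own description of hypotension makes overdispersion likely for that event, though it does not prove it.

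The assumed range runs from essentially no inflation without heterogeneity to rejection of a true null in about half of trials at the highest mean and dispersion examined. It rests on gamma heterogeneity, 8 per arm and a two-sided 5% test.

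This should be fixed before analysis. It does not invalidate the any-event or serious-hypotension comparisons.

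**What to change.** In section 7.4.1, state that for rates of repeatable events the participant is the unit of analysis, and pre-specify one of two methods:

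- Poisson regression on arm and LVEF stratum, with the standard error scaled by the Pearson dispersion (not below 1) and a t reference on the residual degrees of freedom (13 if all 16 participants contribute). This gives the interval that later planning needs.
- A permutation test of participant rates within LVEF stratum. This can still be computed when one arm has no events.

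Use log follow-up time, or log number of dialysis sessions reviewed, as the offset (or as the denominator of the participant rate). Section 7.3 expects up to 10% to withdraw, so exposure will differ. State which events are counted as repeatable and what constitutes one event.

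Do not rely on an uncorrected sandwich variance or on negative binomial regression with 16 participants. A baseline hypotension covariate is optional.

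The cost is a few lines of SAP text and code. Intervals widen by about √φ, and slightly more from the t multiplier (2.16 on 13 df rather than 1.96). At low event counts the scaled test is conservative. The required fix needs no new participants or procedures, but the number of sessions reviewed must be recorded if it serves as the denominator.

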7.4.2 Secondary Analyses

A number of secondary analyses will be conducted to evaluate the secondary efficacy outcomes. Secondary efficacy parameters include angiogenesis inhibitor concentration, circulating markers of

fibrosis, additional echocardiographic parameters, and additional PET parameters including change in resting and hyperemic myocardial blood flows between baseline and 26 weeks and change in LVMI between 0 and 26 weeks. Analysis for these secondary outcomes will be similar to that for the primary outcome. Distribution of the secondary parameters will be examined and appropriate transformation will be applied. Because beta blockers may have effects on cardiac function, analyses will be performed to explore differences in efficacy outcomes between participants with and without beta blocker use at baseline.

7.4.3 Interim Analysis

No interim analysis is planned.

8 Safety and Adverse Events

8.1 Definitions

Definitions are per the January 2007 Guidance on Reviewing and Reporting Unanticipated Problems Involving Risks to Participants or Others and Adverse Events, Office on Human Research Protection (OHRP) Guidance. <http://www.hhs.gov/ohrp/policy/advevntguid.html>

8.1.1 Adverse Event

An *adverse event (AE)* is any untoward or unfavorable medical occurrence in a human study participant, including any abnormal sign (for example, abnormal physical examination or laboratory finding), symptom, or disease, temporally associated with the participant's involvement in the research, whether or not considered related to the participant's participation in the research.

8.1.2 Serious Adverse Event

A *serious adverse event (SAE)* is any AE that is:

- fatal or results in death
- life-threatening
- requires or prolongs hospital stay
- results in persistent or significant disability or incapacity
- results in congenital anomalies or birth defects
- an important medical event*

*Important medical events are those that may not be immediately life threatening, but are clearly of major clinical significance.

8.1.3 Unanticipated Problem Involving Risk to Participants or Others

An Unanticipated Problem is any incident, experience, or outcome that meets all of the following criteria:

- it is unexpected (in terms of nature, severity, or frequency) given the research procedures that are described in the IRB-approved research protocol and informed consent document and the characteristics of the participant population being studied;

- it is related or possibly related to participation in the research; possibly related means that there is a reasonable possibility that the incident, experience or outcome may have been caused by the procedures involved in the research, and
- it suggests that the research places participants or others at a greater risk of harm (including physical, psychological, economic, or social harm) related to the research than was previously known or recognized.

8.1.4 Pre-Existing Condition

A preexisting condition is one that is present at the start of the study. A preexisting condition will be recorded as an adverse event if the frequency, intensity, or the character of the condition worsens during the study period.

8.2 Adverse Event Reporting Period

The study period during which adverse events must be tracked and reported is defined as the period from the initiation of study procedures to study completion.

8.2.1 Post-study Adverse Events

All unresolved adverse events will be followed by the investigator until the events are resolved, the participant is lost to follow-up, or the adverse event is otherwise explained. At the last scheduled visit, the investigator will instruct each participant to report any subsequent event(s) that the participant, or the participant's personal physician, believes might reasonably be related to participation in this study. The investigator will notify the Data Coordinating Center (DCC) of any death or adverse event occurring at any time after a participant has discontinued or terminated study participation that may reasonably be related to the study.

8.3 Recording of Adverse Events

At each contact with the participant, the investigator or site designee will seek information on adverse events by specific questioning and, as appropriate, by examination. Information on adverse events will be recorded in the source document, and also on the adverse event log case report form (CRF). All signs, symptoms, and abnormal diagnostic procedure results relating to the same event will be recorded under one diagnosis name.

8.3.1 Anticipated Adverse Events

The following adverse events are anticipated in the hemodialysis population and are not considered Unanticipated Problems. Note that the designation as "Anticipated" does not imply that the event is not an SAE but relates to the regulatory definition of Unanticipated Problems as provided in **Section 8.1.3**.

- Death
- Coronary Ischemia including:
 - Unstable angina
 - Acute MI
 - Coronary revascularization
- Heart failure hospitalization or exacerbation

- Cardiac arrest
- Cardiac arrhythmia (ventricular or atrial)
- Peripheral vascular revascularization
- Amputation
- Hypotension
- Vomiting
- Vascular Access Events Including:
 - Catheter exchange, removal or declotting
 - Arteriovenous graft or fistula complications
 - Clotting
 - Stenosis
 - Revascularization
 - Infection
- Infections Including:
 - Pneumonia
 - Bacteremia
 - Hemodialysis vascular access infection

The following adverse events are anticipated in patients treated with ISD, HY:

- Hypotension
- Headache
- Gastrointestinal symptoms including diarrhea, constipation and nausea
- Rash
- Edema
- Flushing
- Nasal congestion
- Light-headedness

